6.2.1. Rationale for Exclusion of Certain Study Candidates

The rationale for the exclusion criteria is as follows:

- Exclusion Criteria [8] to [13] exclude individuals with conditions that may confound safety or efficacy analyses.
- Exclusion Criteria [14] to [23] exclude individuals who are at an increased risk for infections or infectious complications.
- Exclusion Criteria [24] to [29] exclude individuals with previous or concomitant medical conditions that increase the risk for their participation in the study.
- Exclusion Criteria [30] to [44] exclude individuals who are taking or who may take JIA or JIA-U medications or treatments that interfere with the ability to assess the safety and efficacy of baricitinib.
- Exclusion Criteria [45] to [46] exclude individuals with laboratory parameters that may increase the risk for their participation in the study.
- Exclusion Criteria [47] to [53] exclude individuals whose participation in the study may introduce bias.

6.3. Screen Failures

Individuals who do not meet the criteria for participation in this study (screen failure) may be rescreened up to 2 times. The interval between rescreenings should be at least 4 weeks. Each time rescreening is performed the legal representative must sign a new ICF and the child must sign an assent, as applicable. The individual will be assigned a new identification number.

7. Treatments

7.1. Treatments Administered

The dose selection for baricitinib in this patient population is informed by the Phases 2 and 3 data in adults with RA, which demonstrated a positive benefit/risk profile for the 4-mg QD dose. The PK of baricitinib in pediatric patients with JIA will be investigated in Study I4V-MC-JAHV (JAHV), and the doses selected in this study will also be used in Study JAHW (see [Appendix 8](#) for updated dosing based on the current JAHV data).

Adalimumab will be administered as a subcutaneous injection. The first dose of adalimumab will be administered by the research team. All participants or a family member/caregiver will be invited to (self-)administer adalimumab after the first dose, and taught to do this under the procedures in place within each participating center. The first dose they administer may also be under the supervision of the clinical team, who will ensure the appropriateness and accuracy of the technique. If the patient, family member or caregiver do not want to (self-)administer adalimumab, then arrangements will be put in place on an individual basis to ensure that trial medication is administered as prescribed.

[Table JAHW.6](#) shows the treatment regimens.

Table JAHW.6. Treatment Regimens

Treatment Group	Treatments Administered (Intervention name, dosage level, and route of administration)	Authorized as defined by EU Clinical Trial Regulations
Baricitinib 4-mg	Baricitinib 4-mg oral tablet	Authorized in EU and not used according to authorization
	Baricitinib 2-mg/mL oral suspension	Not authorized in EU
Baricitinib 2-mg	Baricitinib 2-mg oral tablet	Authorized in EU and not used according to authorization
	Baricitinib 2-mg/mL oral suspension	Not authorized in EU
Baricitinib 1-mg	Baricitinib 1-mg oral tablet	Not authorized in the EU
	Baricitinib 2-mg/mL oral suspension	Not authorized in the EU
Adalimumab	Adalimumab 20 mg in those weighing <30 kg or 40 mg in those ≥ 30 kg	Authorized and used according to authorization

Note: The oral suspension dose may be administered as 4-mg, 2-mg, 1-mg, and 0.5-mg as needed. The oral suspension contains sorbitol solution (70% sorbitol) at a concentration of 150 mg/mL, which is equivalent to 105 mg of sorbitol per mL. Patients with hereditary fructose intolerance should not exceed 5 mg/kg/day of sorbitol, according to the guideline on “Excipients in the labelling and package leaflet of medicinal products for human use (EMA/CHMP/302620/2017; EMA [WWW]).”

Note: Patients with renal impairment or renal immaturity (defined as eGFR <60 mL/min/1.73 m²) at baseline will have their baricitinib dose reduced by 50%. Patients with renal impairment or renal immaturity who would have received the 2-mg or 1-mg dose will be dose-reduced to 1-mg or 0.5-mg, respectively, using the oral suspension.

The investigator or appointed designee is responsible for the following:

- Explaining the correct use of the investigational agent(s) to the parent or legal guardian

- Verifying that instructions are followed properly
- Maintaining accurate records of investigational product dispensing and collection
- At the end of the study returning all unused medication to Lilly, or its designee, unless the sponsor and sites have agreed all unused medication is to be destroyed by the site, as allowed by local law.

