7.1.1. Packaging and Labeling

The sponsor (or its designee) will supply the following investigational products in accordance with current Good Manufacturing Practice:

- Tablets containing 4-mg of baricitinib
- Tablets containing 2-mg of baricitinib
- Tablets containing 1-mg of baricitinib
- Suspension containing 2-mg/mL of baricitinib
- Vials or syringes of adalimumab for injection

Each tablet has a distinctive shape and color: 4-mg versus 2-mg versus 1-mg. Baricitinib oral suspension (containing 2 mg/mL baricitinib) will be supplied as a ready-to-use oral suspension. Baricitinib oral suspension will be provided in a bottle and doses will be delivered to the patient using a standard oral syringe.

Study interventions will be labeled as appropriate for country requirements.

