7.2. Method of Treatment Assignment

Patients will receive the final age-based dose of baricitinib selected in the PK assessment period of Study JAHV (Section 7.2.1). Pharmacokinetic data from Study JAHV will be provided by age cohort (12 to <18 years, 9 to <12 years, 6 to <9 years, and 2 to <6 years; see [Appendix 8](#) for updated dosing based on the current data). Enrollment in Study JAHW may be restricted to patients represented in the age cohorts for which PK data are available from Study JAHV, until JAHV PK data become available for other age groups.

All patients <6 years of age will receive oral suspension. Patients ≥ 6 to <12 years of age have the option of receiving the oral suspension. Patients >12 years will be supplied tablets only.

- Baricitinib arm: At least 20 patients (MTX-IR and/or bDMARD-IR) evaluable for primary endpoint.
- Adalimumab arm: At least 4 patients evaluable for the primary endpoint.

Assignment to treatment groups will be determined by a computer-generated random sequence using an interactive web-response system (IWRS). The IWRS will be used to assign investigational product to each patient.

Site personnel will confirm that they have located the correct packages by entering a confirmation number found on the packages into the IWRS before dispensing to the patient.

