7.2.1. Selection and Timing of Doses

Baricitinib:

Baricitinib should be administered at approximately the same time each day. Patients will receive the final age-based dose of baricitinib selected in the PK assessment period of Study JAHV. Based on PBPK modeling, this is expected to be 4-mg for patients ≥ 9 to < 18 years of age and 2-mg for patients < 9 years of age, in order to produce exposures similar to those in adults after 4-mg QD administration; see [Appendix 8](#) for updated dosing based on the current data. Refer to Section [5.5](#) for additional information.

Adalimumab:

Adalimumab will be administered as a subcutaneous injection once every 2 weeks. The dose will be based on body weight: 20 mg every 2 weeks for participants weighing < 30 kg, or 40 mg every 2 weeks for patients weighing ≥ 30 kg (adalimumab SmPC).

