6 to <9 years old	2 mg (based on predicted data – to be confirmed with observed data)
2 to <6 years old	2 mg ^a

Abbreviations: OLLI = open-label lead-in; PK = pharmacokinetic; QD = once daily.

^a To be confirmed after evaluating data from patients aged 6 to <9 years.

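### As written, a child under 6 with hereditary fructose intolerance, weight below 21 kg and eGFR of 60 or more has no baricitinib regimen that meets the protocol's own sorbitol limit

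*Protocol*

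**What the plan says.** - **Limit.** The note to Table JAHW.6 (Protocol 7.1) states: "Patients with hereditary fructose intolerance should not exceed 5 mg/kg/day of sorbitol". It cites an EMA excipient guideline. For the suspension's sorbitol content it gives 150 mg/mL of a 70% solution, "which is equivalent to 105 mg of sorbitol per mL".
- **Strength.** Section 7.1.1 lists "Suspension containing 2-mg/mL of baricitinib".
- **Formulation.** Section 7.2: "All patients <6 years of age will receive oral suspension". From 6 to under 12, patients "years of age have the option of receiving the oral suspension", so tablets are open to them.
- **Dose.** Section 7.2.1 gives the expected dose as "2-mg for patients < 9 years of age". SAP 5.3.1 also gives 2 mg under 6. The dosing table in Appendix 8 shows 2 mg for ages 2 to <6 with the footnote "To be confirmed after evaluating data from patients aged 6 to <9 years".
- **Dose changes.** The one stated reduction halves the dose when baseline eGFR is below 60 mL/min/1.73 m² (7.1, 7.4). Section 7.4 fixes dose and formulation through Part A and offers tablets in Part B once a child is past 6.
- **Cohort opening.** Section 7.2 adds: "Enrollment in Study JAHW may be restricted to patients represented in the age cohorts for which PK data are available from Study JAHV".
- **Eligibility.** Nothing in 6.2 names hereditary fructose intolerance or sorbitol, or sets a minimum weight. Exclusion [25] leaves serious illness to the investigator's judgement of risk. Exclusion [42] concerns a hypersensitivity to an excipient that the child has already experienced.

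**The concern.** The limit depends on body weight, but the baricitinib dose is set by age and, under 6, the formulation is set by age as well. In a small enough child the two must collide, and the plan has no rule for that case.

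A child with the condition could pass every named criterion and be assigned baricitinib, by randomisation if in the MTX-IR group (5.1.2). If the site then applies the note, the assigned child has no permitted regimen. If the site overlooks it, the child is dosed above a stated safety limit for the 24 weeks of Part A, and into Part B until tablets become available after age 6 or weight reaches 21 kg.

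Children of this size are foreseen. Appendix 7 has a blood-sampling band for weight below 18 kg, and SAP Table JAHW.6.2 has a weight category below 20 kg.

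**Working it through.** **Inputs.** Sorbitol solution 150 mg/mL at 70%, and the limit of 5 mg/kg/day (note to Table JAHW.6). Suspension strength 2 mg/mL (7.1.1). Doses from 7.2.1, Appendix 8 and the renal note in 7.1.

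**The plan's own figure.** 150 × 0.70 = 105 mg sorbitol per mL. This reproduces the stated content.

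**Formulas.** Volume (mL) = dose / 2. Sorbitol (mg/day) = volume × 105. Minimum weight that meets the limit (kg) = sorbitol / 5.

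| Daily dose | Volume | Sorbitol | Minimum weight |
|---|---|---|---|
| 1 mg | 1 / 2 = 0.5 mL | 0.5 × 105 = 52.5 mg | 52.5 / 5 = 10.5 kg |
| 2 mg | 2 / 2 = 1 mL | 1 × 105 = 105 mg | 105 / 5 = 21 kg |
| 4 mg | 4 / 2 = 2 mL | 2 × 105 = 210 mg | 210 / 5 = 42 kg |

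**Size of the excess at 2 mg of suspension**

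| Weight | Sorbitol (mg/kg/day) | Multiple of the limit |
|---|---|---|
| 12 kg | 105 / 12 = 8.75 | 1.75 |
| 15 kg | 105 / 15 = 7.0 | 1.40 |
| 18 kg | 105 / 18 = 5.83 | 1.17 |
| 20 kg | 105 / 20 = 5.25 | 1.05 |
| 21 kg | 105 / 21 = 5.0 | 1.00 (met) |
| 25 kg | 105 / 25 = 4.2 | 0.84 (met) |

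**Is there a compliant route in the text for an affected child under 6 and under 21 kg?**

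1. Tablets: not offered under 6 (7.2).
2. Lower dose: the note lists 1 mg and 0.5 mg suspension doses for use as needed, but no rule ties them to this condition or to weight. The only stated trigger is eGFR below 60. With that reduction the dose is 1 mg and the limit is met from 10.5 kg, which is why the point is confined to eGFR of 60 or more.
3. Ineligibility: exclusion [25] may be used but is discretionary. Exclusion [42] needs a past hypersensitivity reaction, and a hereditary metabolic intolerance is not that. Neither applies 5 mg/kg/day.

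So the limit is stated, but no stated rule carries it out.

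**The case against.** The strongest reply is that the note is itself the instruction. It gives the sorbitol content and the cap together, so a site has what it needs, and a specific cap naturally overrides a general assignment rule. Exclusion [25] gives the investigator a way to keep the child out, and medical history and eligibility are reviewed before the first dose. On this view only a follow-on instruction is missing. Part of this stands: a site that reads the note should not give the dose. But the note does not say what to do instead, and exclusion [25] leaves sites free to decide differently.

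A reader might infer more than the documents support:

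- *That the protocol firmly requires an over-limit dose, or that children are receiving one.* Section 7.2.1 only expects 2 mg, Appendix 8 marks it as unconfirmed at ages 2 to <6, enrolment may be restricted to age cohorts with PK data, and the note forbids exceeding the cap.
- *That a stated figure is wrong.* Each one checks.
- *That children of 6 or older face the same conflict.* On the usual 2 mg or 4 mg dose they can take tablets, so for them it is a choice of formulation.
- *That harm is shown.* The documents give no estimate of risk at 1.05 to 1.75 times the limit.

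It is also fair to object that excluding the child loses someone who might have been randomised to adalimumab and never taken sorbitol. That is a real cost of the fix.

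**Conclusion.** The point holds in a narrow form and is minor. On the current text, the regimen for a child under 6 on baricitinib with eGFR of 60 or more is 2 mg of suspension, or 105 mg of sorbitol a day. With hereditary fructose intolerance and a weight below 21 kg, that exceeds the protocol's own limit, and no stated tablet option, dose reduction or named criterion gives a compliant regimen.

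This rests on two conditions: the 2 to <6 cohort is open, and 2 mg is retained for it. If the dose were settled at 1 mg, the threshold would fall to 10.5 kg. The documents give no frequency for the condition, so the number affected cannot be derived; it will be few and may be none. Sample size, decision rules and analyses are untouched. The reason to act is that this is a safety limit the sponsor wrote into the protocol, and closing the gap is cheap.

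**What to change.** 1. **Section 6.2, cross-referenced from the note to Table JAHW.6.** Add that a child with hereditary fructose intolerance who can only receive suspension is not eligible if baseline weight is below the minimum for the dose that child would receive: 21 kg for 2 mg, 10.5 kg for 1 mg. Check this before treatment assignment, and update the minimum if the under-6 dose changes. Exclusion [10] is a drafting model: it already keeps out a child who cannot take one of the two arms, with an exception where assignment to the other arm is certain.
2. **Note to Table JAHW.6.** Add that affected children aged 6 or older take tablets unless their weight meets the minimum for the suspension dose (21 kg for 2 mg, 42 kg for 4 mg), rechecked when the dose rises to 4 mg in Part B. This is a safeguard on a choice of formulation.

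**Cost.** One extra check, using medical history and weight that the Schedule of Activities already collects at screening or baseline, and the possible loss of a very rare patient, including one who might have been randomised to adalimumab. The analysis does not change.

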7.1.1. Packaging and Labeling

The sponsor (or its designee) will supply the following investigational products in accordance with current Good Manufacturing Practice:

- Tablets containing 4-mg of baricitinib
- Tablets containing 2-mg of baricitinib
- Tablets containing 1-mg of baricitinib
- Suspension containing 2-mg/mL of baricitinib
- Vials or syringes of adalimumab for injection

Each tablet has a distinctive shape and color: 4-mg versus 2-mg versus 1-mg. Baricitinib oral suspension (containing 2 mg/mL baricitinib) will be supplied as a ready-to-use oral suspension. Baricitinib oral suspension will be provided in a bottle and doses will be delivered to the patient using a standard oral syringe.

Study interventions will be labeled as appropriate for country requirements.

7.2. Method of Treatment Assignment

Patients will receive the final age-based dose of baricitinib selected in the PK assessment period of Study JAHV (Section 7.2.1). Pharmacokinetic data from Study JAHV will be provided by age cohort (12 to <18 years, 9 to <12 years, 6 to <9 years, and 2 to <6 years; see [Appendix 8](#) for updated dosing based on the current data). Enrollment in Study JAHW may be restricted to patients represented in the age cohorts for which PK data are available from Study JAHV, until JAHV PK data become available for other age groups.

All patients <6 years of age will receive oral suspension. Patients ≥ 6 to <12 years of age have the option of receiving the oral suspension. Patients >12 years will be supplied tablets only.

- Baricitinib arm: At least 20 patients (MTX-IR and/or bDMARD-IR) evaluable for primary endpoint.
- Adalimumab arm: At least 4 patients evaluable for the primary endpoint.

Assignment to treatment groups will be determined by a computer-generated random sequence using an interactive web-response system (IWRS). The IWRS will be used to assign investigational product to each patient.

Site personnel will confirm that they have located the correct packages by entering a confirmation number found on the packages into the IWRS before dispensing to the patient.

7.2.1. Selection and Timing of Doses

Baricitinib:

Baricitinib should be administered at approximately the same time each day. Patients will receive the final age-based dose of baricitinib selected in the PK assessment period of Study JAHV. Based on PBPK modeling, this is expected to be 4-mg for patients ≥ 9 to < 18 years of age and 2-mg for patients < 9 years of age, in order to produce exposures similar to those in adults after 4-mg QD administration; see [Appendix 8](#) for updated dosing based on the current data. Refer to Section [5.5](#) for additional information.

Adalimumab:

Adalimumab will be administered as a subcutaneous injection once every 2 weeks. The dose will be based on body weight: 20 mg every 2 weeks for participants weighing < 30 kg, or 40 mg every 2 weeks for patients weighing ≥ 30 kg (adalimumab SmPC).

7.3. Blinding

This is an open-label study.

7.4. Dosage Modification

Baricitinib:

The baricitinib dose and formulation for an individual patient will not change during Part A of this study. During Part B, as patients age over 9 years old, they will receive baricitinib 4 mg at their next scheduled visit, and as patients age over 6 years old, they will have the option of receiving tablets instead of suspension. For patients who progress to the ≥ 18 years age group, their current dose will be maintained.

The baricitinib dose will be reduced by 50% in patients with renal impairment (defined as eGFR < 60 mL/min/1.73 m²) at baseline.

Adalimumab:

The adalimumab dose will be based on body weight (20 mg for patients weighing < 30 kg or 40 mg for patients weighing ≥ 30 kg; adalimumab SmPC). Dose modifications are NOT permitted in patients whose body weight changes from less than 30 kg to greater than 30 kg or from greater than 30 kg to less than 30 kg during Part A.

7.5. Preparation/Handling/Storage/Accountability

All investigational products (used and partially used) will be returned to the sponsor or destroyed at site level with the sponsor's written approval. In some cases, sites may destroy the material if, during the investigative site selection, the evaluator has verified and documented that the site has appropriate facilities and written procedures to dispose of clinical study materials.

Investigators and site personnel will follow storage and handling instructions on the investigational product packaging.

Only participants enrolled in the study, or their parent or legal guardian, may receive investigational product and only authorized site staff may supply investigational product. All investigational products should be stored in an environmentally controlled and monitored (manual or automated) area in accordance with the labeled storage conditions with access limited to the investigator and authorized site staff.

The investigator is responsible for investigational product accountability, reconciliation, and record maintenance (such as receipt, reconciliation, and final disposition records).

7.6. Treatment Compliance

Patient compliance with study medication will be assessed during the treatment period of Part A and Part B per the Schedule of Activities.

Patients treated with baricitinib or adalimumab will be considered noncompliant if they miss $\geq 20\%$ of the prescribed doses during the study (unless the patient's investigational product was withheld by the investigator for safety reasons). For adalimumab, a patient will be considered significantly noncompliant if his or her study medication compliance rate is $< 80\%$ or if there are any consecutive missed injections, unless the patient's investigational product was withheld by the investigator for safety reasons.

Similarly, patients will be considered noncompliant if they are judged by the investigator to have intentionally or repeatedly taken more than the prescribed amount of study medication. Patients found to be noncompliant with the investigational product should be assessed to determine the reason for noncompliance and educated and/or managed as deemed appropriate by the investigator to improve compliance.

Patients will be counseled by study staff on the importance of taking the investigational product as prescribed, as appropriate.

Patient compliance will be further defined in the statistical analysis plan (SAP).

7.7. Concomitant Therapy

All concomitant medication taken during the study must be recorded on the Concomitant Medication electronic case report form (eCRF).

Patients will be instructed to consult the investigator or other appropriate study personnel at the site before taking any new medications or supplements during the study.

Additional drugs are to be avoided unless required to treat AEs or for the treatment of an ongoing medical condition. If the need for other concomitant medications arises, discontinuation of the patient from the investigational product or the study will be at the discretion of the investigator in consultation with Lilly or its designee (Section 8.2).

Treatment with concomitant therapies during the study is permitted only as described below and in [Table JAHW.7](#). During Part A, the dosages of concomitant treatment may only be adjusted for safety reasons, with the exception of topical corticosteroid eye drops.

Methotrexate, mycophenolate mofetil, and csDMARDs:

- Chronic stable use of MTX is permitted up to a maximum dose of 25 mg/m²/week throughout the study.
- Patients must be on a stable dose of MTX for at least 4 weeks prior to screening, and remain on the same dose throughout Part A.
- During Part B, MTX may be initiated or the dose increased, decreased, or discontinued, at the discretion of the investigator, and according to local clinical practice.
- Local standard of care should be followed for concomitant administration of folic acid.
- Chronic stable use of csDMARDs (other than MTX) and mycophenolate mofetil is permitted. Patients must be on a stable dose for at least 4 weeks prior to screening.
- During Part A, initiation of new csDMARDs and/or increases in dose are not permitted.
- During Part B, other csDMARDs or mycophenolate mofetil may be initiated, or the dose increased, decreased, or discontinued, at the discretion of the investigator, and according to local clinical practice.
- Concomitant use of >2 csDMARDs (including MTX) is not allowed.

Topical steroid eye drops:

- Topical steroid eye drops, with a maximum of 4 drops/day per eye at screening, are permitted as background therapy during the study. The dose must have been stable for at least 2 weeks prior to screening.
- Steroid drop tapering is recommended as shown in the following table:

Study Interval	Dose Reduction
Week 0–Week 4	No dose changes permitted
Week 4–Week 8	Reduce drops to a maximum of 3 drops/day per eye
Week 8–Week 20	Reduce drops to a maximum of 2 drops/day per eye
Week 20–Week 24	No dose changes permitted
Week 24 onward (Part B)	Reduce drops at the discretion of the treating clinician to any dose, including zero

- If tapering is not tolerated during Part A or Part B, the number of drops can be increased up to the number received at screening.
- The topical steroid eye drop formulation (Maxidex, Predforte, or equivalent) should remain the same as that used at screening and will not change for individual patients throughout Part A, unless required for safety or supply issues; the formulation may be changed during Part B.

Oral corticosteroids:

- Chronic stable use of oral corticosteroids is permitted and defined as daily doses of ≤10 mg/day or 0.2 mg/kg/day prednisone equivalent, whichever is less.
- Patients must be on a stable dose for at least 2 weeks prior to screening and 4 weeks prior to baseline, and remain on the same dose throughout Part A, except for treatment of an AE.

- During Part B, oral corticosteroids may be initiated, or the dose increased, decreased, or discontinued, at the discretion of the investigator.

Intra-articular corticosteroid joint injections:

- A maximum of 8 injections are permitted per year.
- No more than 2 injections are permitted in a single session.
- No injections are permitted within 4 weeks prior to Visit 2.

Intraocular corticosteroid injections:

- Depot peri-ocular, peri-ocular or intraocular corticosteroid injections are not permitted within 30 days prior to Visit 2 or during Part A.
- Intraocular or peri-ocular corticosteroid injections are permitted during Part B at the discretion of the investigator.

Other corticosteroids

- With the exception of oral and intra-articular corticosteroids, patients should not receive other systemic corticosteroids during Part A, including intramuscular corticosteroids.
- During Part B, other systemic steroids may be administered; however, the daily dose should be ≤ 10 mg/day or 0.2 mg/kg/day prednisone equivalent, whichever is less.
- Topical, intranasal, and inhaled corticosteroids are permitted.

Analgesics and NSAIDs

- Chronic stable use of NSAIDs and analgesics is permitted. Patients must be on a stable dose for at least 1 week prior to Visit 2.
- Increases in dose and/or introduction of new NSAIDs and analgesics are not permitted during Part A, except for treatment of an AE.
- During Part B, other analgesics or NSAIDs may be initiated or dose may be increased at the discretion of the investigator.
- Dose reductions and/or termination of NSAIDs and analgesics are permitted.

Permitted analgesics include

- acetaminophen
- NSAIDs, e.g. ibuprofen
- cyclooxygenase-2 inhibitors, e.g. celecoxib
- opioids, e.g. tramadol, codeine, or morphine
- local anaesthetics, e.g. lidocaine, and
- topical anaesthetics, e.g. EMLA cream.

The following therapies will not be permitted during the course of the study as specified in the exclusion criteria (Section 6.2):

- bDMARDs
- Intraocular steroid implants
- Intraocular disease modifying agents, including anti-VEGF injections
- Strong OAT3 inhibitors, e.g. probenecid
- Interferon therapy
- Live vaccine within 28 days prior to baseline or expect to need/receive live vaccine during the course of the study (except booster immunization with attenuated vaccine for MMR or VZV). Booster vaccination with attenuated vaccine for MMR or VZV may be considered if it is essential based on the local guideline and/or in the opinion of the investigator.

Table JAHW.7. Concomitant JIA Therapies

Drug Class	As Needed	Chronic Use	Conditions for Use During Part A
MTX ^a	No	Yes	
 • Maximum of 25 mg/m²/week. • Stable dose is required for at least 4 weeks prior to screening. • Must continue on same dose throughout Part A. • May initiate, increase or decrease the dose, or discontinue during Part B.
csDMARDs other than MTX ^a	No	Yes	
 • Stable dose is required for at least 4 weeks prior to screening. • Must continue on same dose throughout Part A. • May initiate, increase or decrease dose, or discontinue during Part B. • Maximum of 2 concomitant csDMARDs (including MTX).
Mycophenolate mofetil	No	Yes	
 • Stable dose is required for at least 4 weeks prior to screening. • Must continue on same dose throughout Part A. • May initiate, increase or decrease the dose, or discontinue during Part B.
Topical steroid eye drops	No	Yes	
 • Maximum of 4 drops/day per eye at screening. • Stable dose is required for at least 2 weeks prior to screening. • In Part A, drops may be tapered between Week 4 through Week 20. • In Part B, drops may be tapered after Week 24 to any dose, including zero. • Formulation may not change during Part A, but may change during Part B.
Oral corticosteroids	No	Yes	
 • Maximum dose of 10 mg/day or 0.2 mg/kg/day prednisone equivalent, whichever is less. • Stable dose is required for at least 2 weeks prior to screening and 4 weeks prior to baseline. • Must continue on same dose throughout Part A, except for treatment of an AE. • May initiate, increase or decrease dose, or discontinue during Part B.
Intra-articular corticosteroid joint injections	No	No	
 • Maximum of 8 injections per year. • Maximum of 2 injections in a single session. • Not permitted within 4 weeks prior to Visit 2.
Intraocular corticosteroid injections	No	No	
 • Not permitted within 30 days prior to Visit 2. • Not permitted during Part A. • Permitted during Part B.
Systemic corticosteroids (other than oral and intra-articular)	No	Yes	
 • Not permitted during Part A. • Permitted during Part B at a maximum dose of 10 mg/day or 0.2 mg/kg/day prednisone equivalent, whichever is less.
Analgesics & NSAIDs	No	Yes	
 • Stable dose is required for at least 1 week prior to Visit 2. • Must continue on same dose throughout Part A, except for treatment of an AE. • May initiate, increase or decrease dose, or discontinue during Part B.

Abbreviations: csDMARD = conventional synthetic disease-modifying antirheumatic drug; MTX = methotrexate; NSAID = nonsteroidal anti-inflammatory drug.

^a Concomitant use of >2 of any csDMARDs (including MTX) is not allowed.

